## 10.0 Study Design / Methods

This study will be a prospective, single-center, single-blind randomized controlled trial. Participants will be randomized by using a stratified randomization technique, stratified by sex into two groups:

- 1) continuous adductor canal block alone (ACB Only) or
- 2) continuous adductor canal block with iPACK block (ACB + iPACK).

Preoperative: Adult participants and pediatric patients >70kg will receive 1g Tylenol and 1-2mg midazolam and up to 20mcg of dexmedetomidine for preprocedure anxiolysis. Patients between 12 and 18 years old will receive Tylenol with a dose based on weight (Table 1), and 1-2mg midazolam and up to 20mcg of dexmedetomidine.

Table 1. Tylenol Dosage Based on Weight for Pediatrics		
Weight	Dosage	
≥70kg	1,000mg	
45-70kg	650mg	
<45kg	500mg	

All participants will receive the continuous adductor canal block which consists of 20cc of 0.25% plain ropivacaine and will be given followed by placement of an OnQ pump infusing 0.2% ropivacaine at 6cc/hr. (4cc/hr. for participants less than 60Kg).

Those who are randomized to the ABC + iPACK group will receive an additional block consisting of 20cc of 0.25% Ropivacaine placed in the popliteal fossa between the popliteal artery and the posterior aspect of the capsule of the knee joint.

Participants randomized to the ACB-only group will receive a skin wheal at the same site where the iPACK block would have been placed in an effort to maintain the blind.

Perioperative: Participants will be appropriately sedated as per clinical care.

Postoperative: Participants will be given 0.2mg hydromorphone every 8 minutes as needed for pain, and 5mg of oxycodone may be administered adjunctively as needed if pan scores remain elevated after intravenous hydromorphone

Post-discharge: Participants will be instructed to schedule two post-operative follow up appointments with their surgeon as well as physical therapy. They will also be prescribed the following medication regimen after discharge:

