### 11.0 Data Management

- The study will be a double-blinded randomized controlled trial of participants undergoing ACL reconstruction at one academic medical center. Although the anesthesiologist administering the block will not be blinded, the surgeons, participants, and study statistician will be blinded to treatment assignment. Participants will be randomized to receive either ACB or ACB + iPACK block. We will use stratified randomization, stratifying on biologic sex, to ensure similar distributions of male/female participants in each treatment arm the same.
- The primary outcomes of interest are participant reported postoperative pain over time and quadricep strength based on the leg raise and knee extension test. Postoperative VAS pain score reported as average, worst, and least pain will be collected on post-op day 0 (after 12pm), 1 (prior to 12 pm and after 12 pm), and 2 (before 12 pm). The association between postoperative pain with block type will be evaluated using a series of linear mixed models evaluating average pain, worst pain, and least pain as dependent variables. Models will include fixed effects for preoperative pain score, block type, postoperative time, and the interaction between block type and post-operative time and a random subject effect to account for correlation between pain scores collected on the same subject over time. Model assumptions will be checked graphically, and transformations will be considered as needed. The difference in patient reported pain between block type by post-operative time and pain score type will be evaluated using a series of linear contrasts. A similar study

by Amer  $(2018)^1$  comparing combined Adductor Canal and iPACK Blocks versus combined Adductor Canal and Periarticular Injection blocks for pain management in ACL Reconstruction Surgery found a difference in VAS pain scores of 1.5 between 0 to 8 hours post-op and standard deviation in VAS pain of 2.5 units. A sample size of n=35 participants per treatment arm (70 total) with at least 3 measures of pain provides 80% power to detect a difference in pain score of 2 units at significance level  $\alpha=0.004$  (Bonferroni corrected for 4 comparisons) and assuming a compound symmetric covariance structure with a conservative standard deviation = 3.0 and correlation within subject is  $\rho=0.33$ . We will enroll 41 participants (82 total) in each arm to allow for up to 20% attrition.

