- Secondary outcomes include cumulative post-operative opiate consumption over time (POD 0 pm, 1 am/pm, and 2 am), and difference in range of motion between surgical and non-surgical leg at first clinic visit (7-21 days post-op) and 6 weeks PO. Associations between these secondary outcomes with block type will be evaluated using a linear mixed approach. Similar to the primary outcome, models will include fixed effects for type, time, and the interaction between block type and time. The model for cumulative opiate consumption will also include a fixed effect for intra-operative opiates received and the model for range of motion will include a fixed effect for pre-operative difference in range of motion between surgical and non-surgical leg.
- All data will be kept on a password protected MUSC server and in a REDCap database. All paper data sheets will be kept in a locked cabinet, in a locked office that only IRB approved study team members have access to. Participants will be given a study ID number that will be used to identify them throughout the study.

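### Randomisation is stratified by sex but no analysis model includes sex; if sex predicts outcome and balance is achieved, standard errors are slightly too wide

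*Combined protocol and SAP*

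**What the plan says.** Section 10.0 (Study Design / Methods) sets the allocation method: "Participants will be randomized by using a stratified randomization technique, stratified by sex into two groups". Section 11.0 (Data Management) repeats it and gives the purpose: "We will use stratified randomization, stratifying on biologic sex, to ensure similar distributions of male/female participants in each treatment arm". No other stratification factor is named, and no block size is given.

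For average, worst and least pain, section 11.0 specifies linear mixed models with a random subject effect: "Models will include fixed effects for preoperative pain score, block type, postoperative time, and the interaction between block type and post-operative time". The treatment comparison is made time by time: "The difference in patient reported pain between block type by post-operative time and pain score type will be evaluated" by linear contrasts.

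For the secondary outcomes, the same section says: "Similar to the primary outcome, models will include fixed effects for type, time, and the interaction between block type and time". One covariate is then added to each. For opioids: "The model for cumulative opiate consumption will also include a fixed effect for intra-operative opiates received". For movement: "the model for range of motion will include a fixed effect for pre-operative difference in range of motion between surgical and non-surgical leg".

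Sex appears in none of these lists. The plan does not explain the omission and does not provide a sensitivity analysis adjusted for sex.

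**The concern.** Choosing sex as the sole stratifier suggests that the sponsor thought it might be prognostic. Balanced allocation within sex takes between-sex variation out of the difference between blocks, but a model without sex still leaves that variation in its error term. What follows depends on two conditions.

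1. Sex predicts the outcome beyond the covariates already in the model.
2. Allocation is actually balanced within sex, as section 11.0 intends.

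If both hold, the reported standard errors are too wide, the tests reject less often than their nominal level, and confidence intervals are wider than they need to be. If only the first holds, the standard errors are valid and the loss is only the precision that adjustment would have brought. If the first fails, nothing is lost. In no case is the block effect biased or type I error inflated.

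**Working it through.** **Inputs from section 11.0.** Difference 2 units; SD 3.0; compound symmetry with within-subject correlation 0.33; at least 3 measures; 35 evaluable participants per arm; alpha 0.004, taken as two-sided (z = 2.878).

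**Reproducing the plan's sample size.** The variance of a subject's mean of 3 measures is 9 × (1 + 2 × 0.33)/3 = 4.98 (SD 2.232).

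- n per arm = 2 × 4.98 × (2.878 + 0.842)²/2² = 34.5, rounded up to 35, as stated.
- At 35 per arm the standard error is 2.232 × √(2/35) = 0.533, so λ = 2/0.533 = 3.749. Power is Φ(3.749 − 2.878) = 80.8% by the normal approximation, or 77.5% by noncentral t.

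The stated figure therefore reproduces with no sex term, and it does so for the mean of 3 measures.

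**Assumed inputs.** The documents give no sex effect and no sex split. I take a sex difference d of 0.5, 1 or 2 points, constant over time and not absorbed by preoperative pain, with a 50/50 split (p = 0.5). The variances above are treated as those remaining after the listed covariates. A d of 2 equals the whole target treatment effect and is an upper extreme.

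**Formulas, with arms balanced within sex.**

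- Share of variance due to sex: R² = p(1 − p)d²/V, with V = 9.0 for a single time and 4.98 for the mean of 3. At p = 0.5 the numerator is 0.0625, 0.25 and 1.0.
- Overstatement of the standard error: 1/√(1 − R²).
- Actual size of the unadjusted test: 2[1 − Φ(2.878/√(1 − R²))].
- Power without sex: Φ((λ − 2.878)/√(1 − R²)). Power with sex: Φ(λ/√(1 − R²) − 2.878).

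| Contrast | d | R² | SE ratio | Actual size at 0.004 | Power without → with sex |
|---|---|---|---|---|---|
| Single time | 0.5 | 0.007 | 1.0035 | 0.0039 | 46.4% → 46.8% |
| Single time | 1 | 0.028 | 1.0142 | 0.0035 | 46.4% → 48.0% |
| Single time | 2 | 0.111 | 1.0607 | 0.0023 | 46.2% → 53.2% |
| Mean of 3 | 0.5 | 0.013 | 1.0063 | 0.0038 | 81.0% → 81.5% |
| Mean of 3 | 1 | 0.050 | 1.0261 | 0.0031 | 81.4% → 83.4% |
| Mean of 3 | 2 | 0.201 | 1.1186 | 0.0013 | 83.5% → 90.6% |

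The single-time rows use λ = 2/(3.0 × √(2/35)) = 2.789. With a 70/30 sex split the SE ratios are 1.0029, 1.0119 and 1.0502 (single time) and 1.0053, 1.0218 and 1.0968 (mean of 3).

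**Simulation check.** In 40,000 trials of 35 per arm, balanced within sex to one patient, the mean of 3 with d = 1 had an actual SD of the estimate of 0.518, against a reported standard error of 0.532 without sex and 0.518 with it. For a single time with d = 1 the values were 0.710, 0.715 and 0.705.

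A separate simulation used permuted blocks of 4 within sex and t-tests on subject means (12,000 null and 4,000 alternative replicates). With d = 1, type I error at 0.004 was 0.0033 without sex and 0.0041 with it, and power was 77.2% against 79.2%. With no sex effect the two analyses agreed within simulation error.

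**The case against.** The strongest reply is that this hardly matters. Any error is towards caution, so it cannot produce a false claim of benefit. The sex effect, the sex split and the block size are all absent from the documents, so every non-zero figure rests on assumption. Preoperative pain is already in the pain model and may absorb part of any sex effect. The only large numbers come from the 2-point case. At the single-time contrast, which is what section 11.0 plans, a 1-point sex difference overstates the standard error by 1.4% by formula. In the simulation it was only about 0.7% (0.715 against 0.710), which is close to undetectable. For opioid use and range of motion no size can be given at all.

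All of that stands, and it limits how strongly the point should be put. It does not remove the omission, alter the direction of the effect, or supply a reason to leave sex out. The balance condition also has to be kept in view: the plan intends balance within sex, but without a stated blocking scheme it cannot be confirmed.

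The reproduced 80.8% should not be read as general reassurance about power. It shows only that omitting sex causes no shortfall. Power for a single-time contrast on the plan's own inputs is about 46%, and adding sex does not cure that.

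**Conclusion.** The point holds as a modest, near-free improvement. The only factor used to stratify randomisation is missing from every model that the plan specifies. With sex differences in pain of 0.5 to 1 point and near balance within sex, the consequence is a standard error 0.3% to 1.4% too wide at a single time (0.6% to 2.6% on the mean of three measures). A nominal 0.004 test would then run at 0.0031 to 0.0039, and about 0.5 to 2 points of power would be forgone. A 2-point sex difference would raise these to 6% or 12% and about 7 points of power, but that is an extreme. If sex has no effect beyond the listed covariates, the cost is nil. The sample-size calculation does not depend on this and needs no change on its account.

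**What to change.** In section 11.0, add sex as a fixed effect to each specified model: average, worst and least pain, cumulative opioid consumption, and range of motion. State this before unblinding, since a covariate added afterwards can look data-driven. Stating the blocking scheme within sex would also let a reader judge whether the intended balance is likely.

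The cost is one term and one degree of freedom per model. No new data are needed, because sex must already be known to allocate within strata.

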#### **Inclusion Criteria**

- Age 12 years and older
- Patients who are scheduled to undergo an ACL reconstruction with quadriceps or BTB graft.

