### All patients ≥ 18 years of age and pediatric patients ≥70kg

- Tylenol 1,000mg q8h
- Naproxen 500mg twice daily
- Oxycodone 5-10mg q4h PRN pain
- Aspirin 325mg daily for DVT prophylaxis

Additionally, participants will be instructed to follow the following bracing and weight bearing instructions:

- Weight bearing as tolerated and no brace for isolated ACL reconstruction, small 2 or less sutures and all inside repair
- Brace for bucketed meniscus with inside out repair, and associated mcl, OR large repaid (more than 3 sutures) 0-90, and weight bearing as tolerated in extension
- Non-weight bearing with brace for meniscus roots, and lateral meniscus tears.

Currently, there is no consensus guidelines for venous thromboembolism prophylaxis in the setting of anterior cruciate ligament reconstruction surgery. Moreover, there is no universally agreed-upon dose for use of aspirin in the postoperative state for VTE prophylaxis. There is current evidence which would suggest aspirin is an effective and safe medication for DVT prophylaxis and other major lower extremity orthopedic surgical procedures. Additionally, current practice patterns would suggest that aspirin is the most commonly utilized VTE prophylaxis following anterior cruciate ligament reconstruction. [8]

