#### **Baseline and Randomization**

After consenting and confirmation of meeting eligibility criteria, the participant will undergo the procedure as scheduled and as standard of care. The participant will be

randomized before they are anesthetized, as the block will be prepared and placed prior to the start of surgery.

If randomized to ACB-Only (Group A) the participant will receive the ACB block first. The injection site is prepared with a sterile solution, an injection of lidocaine is given to numb the area, then using ultrasound guidance a needle is inserted into the adductor canal at the mid-thigh where a catheter is placed to administer the long-acting anesthetic. Next, to maintain the blind, the participant will receive a skin wheal with lidocaine at the same location as Group B has the iPACK block placed.

Table 5. Post-Op Follow Up Assessments			
Outcome Measure	Instrument	Collected	
Pain Rating	Average pain, most pain, least pain from 0-10 POD Days 0-3		
Opioid Consumption	Number of pills taken in time period POD Days 0-3		
Physical Therapy	Range of Motion and terminal knee extension	Postoperative Visit 1 and 2	
Adverse Events	Adverse Events	Throughout enrollment	

If randomized to ACB + iPACK (Group B) the participant will be administered the ACB first as stated above and the iPACK block second. The iPACK block will be placed at the posterior part of the knee. The area will be numbed first using lidocaine, then using ultrasound guidance, a needle will be inserted in the popliteal fossa between the popliteal artery and the capsule of the knee.

Table 4. Baseline and Intraoperative Assessments		
Demographics		
Baseline		
Pre-op meds including opioids in past 24 hours		
Randomization		
Anesthesia intra-op data		
Surgical techniques		
Adverse Events		

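### Planned graft type is in none of the models and the opioid model has no baseline covariate: adding these is a low-cost gain in precision, not the correction of an error

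*Combined protocol and SAP*

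**What the plan says.** **Pain models (Section 11.0, primary outcome).** "Models will include fixed effects for preoperative pain score, block type, postoperative time, and the interaction between block type and post-operative time", with a random subject effect.

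**Secondary models (Section 11.0).** For both secondary outcomes, "models will include fixed effects for type, time, and the interaction between block type and time". Each model then has one further term:
- Opioids: "The model for cumulative opiate consumption will also include a fixed effect for intra-operative opiates received".
- Range of motion: "the model for range of motion will include a fixed effect for pre-operative difference in range of motion between surgical and non-surgical leg".

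**Population.** The inclusion criteria admit "Patients who are scheduled to undergo an ACL reconstruction with quadriceps or BTB graft". Hamstring grafts, allografts and revisions are excluded. Sections 10.0 and 11.0 stratify randomisation by sex only.

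**Data collected.** Table 4 lists "Pre-op meds including opioids in past 24 hours" and, as a general item, "Surgical techniques". It names neither graft nor concomitant repair.

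**Concomitant procedures.** The post-discharge instructions in Section 10.0 set brace and weight-bearing rules by the associated repair, for example "Brace for bucketed meniscus with inside out repair, and associated mcl".

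**The concern.** The trial admits two graft harvests, and neither the randomisation nor any model takes account of which one a participant has. If graft is related to an outcome, that variation stays in the error term, and a chance imbalance in graft between arms goes unadjusted.

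The opioid model is the least well supplied. The plan treats preoperative pain as worth adjusting for in the pain models but not in the opioid model. It collects prior-day opioid use and then puts it in no model. The one extra term in the opioid model, intra-operative opiates, is measured after randomisation and after the block, so that model has no baseline covariate at all.

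What is at stake is the width of the confidence intervals in a trial of about 35 evaluable participants per arm, and the temptation to choose covariates after the data are seen if an imbalance appears.

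**Working it through.** **1. The plan's own figure.** Inputs from Section 11.0: difference 2 units, SD 3.0, within-subject correlation 0.33, 3 measures, alpha 0.004 (two-sided assumed), 35 per arm.

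- Variance of a subject's mean over 3 measures: 9 × (1 + 2 × 0.33)/3 = 4.98, so SD = 2.232.
- SE of the difference between arms: 2.232 × √(2/35) = 0.533.
- Power by the normal approximation: 80.8%; n for 80% power: 35 per arm.

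The stated sample size is reproduced without any of the omitted covariates, so the design does not depend on them.

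**2. Gain from adjustment.** Let R² be the share of variance explained beyond the covariates already planned (assumed; the documents give none), and q the number of covariates added. Then

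effective n = 35 / [(1 − R²) × 68/(68 − q)],

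where 68 = 70 − 2 and the second factor charges the degrees of freedom. Graft alone is q = 1 (pain, range of motion). Graft, preoperative pain and prior-day opioids is q = 3 (opioids).

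| R² | q = 1 | q = 2 | q = 3 | SE ratio, q = 1 |
|---|---|---|---|---|
| 0 | 34.5 | 34.0 | 33.5 | 1.01 |
| 0.05 | 36.3 | 35.8 | 35.2 | 0.98 |
| 0.10 | 38.3 | 37.7 | 37.2 | 0.96 |
| 0.15 | 40.6 | 40.0 | 39.4 | 0.93 |

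The row R² = 0 is the cost if the covariates prove useless: about half a participant per arm for one covariate and one and a half for three.

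**3. The same gain as power for pain** (SD replaced by 2.232 × √(1 − R²), degrees of freedom not charged). At 35 per arm, power goes from 80.8% to 83.4%, 85.9% and 88.3% for R² = 0.05, 0.10 and 0.15. With the stated 20% attrition, 41 × 0.8 = 32.8, about 33 per arm, and power is 77.7%. An R² of 0.05 brings that to 80.4%, and 0.10 to 83.1%.

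**4. What those R² values require of graft alone.** For a binary factor split 50:50 (assumed) with effect g on pain, R² = 0.25 g²/4.98. So R² = 0.05, 0.10 and 0.15 need g = 1.0, 1.4 and 1.7 units. The top of the range would need a graft effect close to the trial's 2-unit target.

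**5. Chance imbalance.** Assume 82 randomised, 41 per arm, 41 of each graft, and ignore the sex strata. The number of quadriceps grafts in one arm is then hypergeometric.

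- P(arms differ by at least 10 percentage points) = 0.377.
- P(arms differ by at least 15 points) = 0.185.

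The consequence is graft effect × imbalance. With an assumed effect of 1 unit, a 10 to 15 point imbalance moves the pain estimate by 0.10 to 0.15 units, against an SE of 0.53 and a target of 2 units.

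**The case against.** **The unadjusted tests are valid.** A reader might infer that a chance excess of one graft, or of braced knees, would bias the comparison. It would not: under randomisation the unadjusted standard error already includes such imbalance. The plan also adjusts each outcome for at least one plausible predictor and narrows surgical variation through eligibility. This stands, and it makes the point an improvement only.

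**No passage says that graft or repair drives pain or opioid use.** This stands too. The tempting claim that these variables determine pain rests on outside knowledge, and the size of the gain rests wholly on an assumed R². Prior-day opioid use may also vary little, since patients on chronic opioid treatment are excluded.

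**Graft is not shown to be already recorded.** "Surgical techniques" may cover it, but that is an inference. The planned graft must nevertheless be known at screening, because eligibility depends on it.

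**Concomitant repair is a poor covariate for the main models.** A reader might argue that blinded surgeons act on pre-existing pathology, so adjusting for repair removes none of the block effect. The documents do not establish this. Randomisation and block come before surgery, so the repair performed may be settled afterwards. No passage says that it depends only on prior pathology. Section 11.0 says surgeons are blinded, while Section 10.0 calls the trial single-blind.

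The repair categories are not clean either. One rule covers two sutures or fewer and another more than three, so exactly three is unassigned. Lateral meniscus tears have a rule with no size limit, so a small all-inside lateral repair fits two rules. The documented link is to brace and weight bearing only. The documents do not say whether motion is measured in the brace, and a 0-90 range does not on its face restrict terminal extension.

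What survives is the narrower point: covariates fixed before randomisation are left out at almost no saving.

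**Conclusion.** The omission is confirmed, and it is a missed efficiency rather than a mistake. Planned graft is a clean covariate for all models because it is scheduled before randomisation. Preoperative pain and prior-day opioid use are clean covariates for the opioid model because both are baseline values.

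The likely gain is modest: a few participants' worth of information per arm if R² lies between 5% and 15%, and a loss of about 0.5 to 1.5 per arm if it is zero. These figures assume the R² range. The imbalance probabilities assume an equal graft mix. The documents support neither a claim of bias nor the inclusion of performed repair in the main models.

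**What to change.** In Section 11.0, before unblinding:

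1. Add planned graft type (quadriceps or BTB, as scheduled before randomisation) as a fixed effect in the pain, opioid and range-of-motion models.
2. Add preoperative pain score and opioid use in the past 24 hours to the opioid model.
3. Confirm that the Table 4 surgical item captures graft type. If it does not, take planned graft from the surgical schedule.
4. Use concomitant repair only in a pre-specified sensitivity analysis for range of motion, based on the planned procedure where known. The overlapping and incomplete repair categories in the post-discharge instructions must be reconciled first.

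The cost is a few lines of analysis text and one degree of freedom in the pain and range-of-motion models, three in the opioid model. No new data are needed if graft is confirmed as captured; otherwise one field is added. Sex, the stratification factor, is also absent from every model; that is a separate matter that the same edit could settle.

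### The only multiplicity method named for the pain contrasts is Bonferroni; Holm's step-down, once the family is defined, keeps the same family-wise error and never declares fewer contrasts

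*Combined protocol and SAP*

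**What the plan says.** All the relevant text is in section 11.0 (Data Management) of the combined protocol and SAP.

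- **Models.** The plan fits a "series of linear mixed models evaluating average pain, worst pain, and least pain as dependent variables". That makes three score types.
- **Times.** The scores "will be collected on post-op day 0 (after 12pm), 1 (prior to 12 pm and after 12 pm), and 2 (before 12 pm"). That makes four times.
- **Contrasts.** The "difference in patient reported pain between block type by post-operative time and pain score type will be evaluated using a series of linear contrasts". Read literally this is 4 × 3 = 12 block contrasts. The sentence gives no significance level, family or adjustment.
- **Sample size.** The calculation takes 35 per arm, each with three or more pain scores, and claims that this "provides 80% power to detect a difference in pain score of 2 units at significance level" of 0.004. The plan labels that level as "Bonferroni corrected for 4 comparisons". It assumes a "conservative standard deviation = 3.0" and within-subject correlation 0.33 under compound symmetry.

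No section names Holm or any other stepwise procedure.

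**The concern.** The trial wants to show at which postoperative times the added iPACK block reduces pain, so several contrasts will be tested together. If each is held to one fixed Bonferroni level, some differences will go undeclared that the same data could support at the same family-wise error rate. Holm tests the smallest p-value at 0.05/k, the next at 0.05/(k−1), and so on up to 0.05, stopping at the first failure. For k = 4 the thresholds are 0.0125, 0.0167, 0.025 and 0.05, where Bonferroni uses 0.0125 throughout. No Holm threshold is below the Bonferroni level, so every Bonferroni rejection is also a Holm rejection. Family-wise control needs no assumption about the correlation between times or score types.

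What is at stake is how many windows can be declared, and not whether the trial finds anything: both procedures hold the smallest p-value to the same level.

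**Working it through.** **Inputs from section 11.0:** 35 per arm, difference 2, SD 3.0, within-subject correlation 0.33 (compound symmetry), at least 3 measures, alpha 0.004, 80% power. **Assumed:** two-sided tests (the plan does not say; two-sided reproduces its n), family-wise level 0.05, and a correlation between score types of 0.5 or 0.8 (not given in the document).

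**1. Reproduce the plan's sample size.** For the mean of 3 measures, SD = 3.0 × √((1 + 2 × 0.33)/3) = 2.232. Then n = 2 × (2.878 + 0.842)² × 2.232²/2² = 34.5, so 35 per arm, with 80.8% power at n = 35 (normal approximation; 77.5% with the noncentral t). The figure reproduces, but for a time-averaged difference.

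**2. Check the alpha against its label.** 0.05/4 = 0.0125, while 0.05/12 = 0.00417, which rounds to 0.004. The stated level fits 12 contrasts (3 scores × 4 times) and the label says 4. If only four contrasts were tested at 0.004, the family-wise error would be at most 4 × 0.004 = 0.016.

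**3. Bonferroni power for a single-time contrast.** Standard error = 3.0 × √(2/35) = 0.717, so the expected z is 2/0.717 = 2.789.
- k = 4: critical value 2.498; power = Φ(2.789 − 2.498) = 61%.
- k = 12: critical value 2.865; power = Φ(2.789 − 2.865) = 47%.

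**4. Bonferroni against Holm.** This used 300,000 simulated draws of correlated normal test statistics per scenario, with correlation 0.33 across times. Simulation error is at most about 0.1 point. Average power is over the contrasts with a true 2-unit difference.

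| Family | Times with a true difference | Average power, Bonferroni → Holm | At least one true difference found |
|---|---|---|---|
| 4 | all four | 61.5% → 71.0% | 92.1% → 92.1% |
| 4 | two | 61.6% → 63.9% | 80.4% → 80.4% |
| 4 | one | 61.6% → 61.7% | 61.6% → 61.7% |
| 12 (score correlation 0.5) | all four | 47.0% → 57.9% | 96.8% → 96.8% |
| 12 (0.5) | two | 46.9% → 50.1% | 88.7% → 88.7% |
| 12 (0.5) | one | 46.9% → 48.0% | 72.1% → 72.1% |

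With score correlation 0.8 the 12-contrast average powers are nearly the same (46.9% → 57.7% with all times affected). In the 4-contrast family with all times affected, the chance of declaring all four rises from 25.1% to 47.3%.

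**5. Error rate.** With no true difference anywhere, family-wise error is identical for the two procedures: 4.7% for 4 contrasts and 3.6% to 4.4% for 12. With two of four times affected it is 2.5% for Bonferroni and 3.8% for Holm. It stayed below 5% in every scenario. In no draw did Bonferroni reject a contrast that Holm did not.

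**The case against.** **The analysis text does not prescribe Bonferroni.** A reader might infer that the plan fixes single-step Bonferroni testing for every contrast. The document does not say so: Bonferroni appears once, as the basis of a planning alpha. Single-step testing is a reasonable inference because no other method is named, but the text fits an analysis with no multiplicity rule almost as well. Either way, a sentence naming the procedure is needed.

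**Bonferroni is valid and has a use.** A reader might also conclude that it sacrifices power for nothing. That goes too far. It gives simple simultaneous intervals that match its tests, which standard Holm does not, and it lets the sample size be computed at one fixed alpha. The plan was sized at its stated level, so it loses nothing against its own target.

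**The gain depends on the pattern of effect.** This stands. The 10 to 11 point gain needs a 2-unit difference at every time and, for 12 contrasts, on every score type. The only prior effect that the plan cites is 1.5 units at 0 to 8 hours, and section 10.0 describes the iPACK as a single injection. An effect confined to early windows is plausible, and the gain would then be small.

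**Holm cannot be applied until the family is fixed.** This also stands. Besides the 4-or-12 conflict, section 11.0 lists quadriceps strength as a primary outcome, section 4.0 sets 12-hour intervals over 72 hours, and Table 6 has seven collections against four times in section 11.0.

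**Conclusion.** The point holds as a recommended improvement. If the contrasts are tested as the sample-size sentence suggests, Holm would declare at least as many at the same family-wise error. The average gain per contrast is about 10 to 11 points if all windows differ by 2 units, about 2 to 3 points if two do, and 0 to 1 point if one does. The chance of finding at least one true difference moves by no more than about 0.1 point.

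These sizes rest on the plan's SD and correlation, the normal approximation, 35 evaluable participants per arm and, for 12 contrasts, an assumed correlation between score types. That Holm never rejects fewer contrasts rests on none of these.

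Two further inferences are not supported. Bonferroni testing would not be an error, because it controls the family-wise rate. Nor does Holm rescue the stated 80% power for single-time contrasts: that figure belongs to a three-measure average, and a single-time contrast at 80% power needs about 63 per arm at 0.004 or 51 at 0.0125.

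**What to change.** In section 11.0, before any outcome data are seen by arm:

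1. Define the primary family: which score types, which times, and whether anything else belongs to it. State its size k.
2. Reconcile k with the alpha in the sample-size sentence. Either the level is 0.05/12 ≈ 0.004 for 12 contrasts, or it is 0.05/4 = 0.0125 for 4. The sentence should not stay as it is.
3. Then add: 'The block-by-time contrasts in this family will be tested with Holm's step-down procedure at two-sided family-wise 0.05; Bonferroni-level simultaneous intervals will be shown.' If k = 12, say that the contrasts are by time and score type.

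The sample size may stay planned at 0.05/k. That is Holm's first-step level, so power per contrast under Holm cannot be lower than planned at that level.

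The cost is a few sentences and no extra participants. The one drawback is that a contrast declared by Holm may have a Bonferroni-level interval that includes zero. The report should say in advance that the Holm result is the test decision and the interval is for description.
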